Subjects will be seen by the study team 90 days +/- 14 days after enrollment to assess their neurologic function using the NIHSS, mood using the PHQ-9, functional status using the modified Rankin Scale, Quality of life using the Euroqol EQ-5D,^{20, 21} healthcare utilization using the Stanford Health Utilization survey,²² whether any other treatment for mental health problems was received (including medication and psychotherapy) and perceived utility of Joyable iCBT for depression as well as perceived barriers to successful use of internet-based CBT.

Table 1. Study measures and timing of assessment

	Baseline	72 hr Call	30 day call	90 day visit
Demographics	X			
Stroke information	X			
SSRI Use	X		X	X
Assess for technical problems		X	X	
NIHSS	X			X
mRS	X		X	X
EQ-5D	X		X	X
SHU				X
PHQ-9	X			X
Semi-Quantitative assessment of perceptions about Internet-based CBT				X

NIHSS=National Institute of Health Stroke Scale, EQ-5D=Euro-Qol 5D, SHU=Stanford Health Utilization survey, PHQ-9=Patient Health Questionnaire 9,

Analysis Plan

The baseline demographic variables of the study population will be summarized using means, medians, and proportions as appropriate. For each subject, we will calculate the total amount of time spent interacting with the Joyable program and the total number of Joyable activities that the patient successfully completed. We will then calculate averages across the study population. These metrics will provide important information on the average “dose” of CBT received. In an exploratory analysis we will look for relationships between baseline clinical and demographic factors and number of activities completed.

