We will calculate the average PHQ-9 score at enrollment and 90 days. We will compare the PHQ-9 score from enrollment to day 90. The statistical power of this test is uncertain. In Table 2 we present estimated study power (with $\alpha=0.05$) across a range of assumptions about both the change in PHQ-9 over time and the standard deviation of the difference in PHQ-9 over time. These calculations show that although this is a small pilot study, we have >80% power to detect a difference in PHQ-9 of 3 or more points across a range of assumptions. The PHQ-9 will also be administered to subjects weekly via through the Joyable program. We will examine whether there are significant changes in score over time using repeated measures analysis (generalized estimating equations, GEE) with PHQ-9 score as the dependent variable and week as the independent variable.

In an exploratory analysis, we will divide patients into two groups based on PHQ-9 at study completion (*high depression symptoms*, defined as median or above and *low depression*

symptoms, defined as below the median score). Healthcare outcomes, including modified Rankin scale, health related quality of life, and healthcare utilization will be compared across groups. We hypothesize that patients with high depression symptoms will have worse functional outcome, lower quality of life, and higher healthcare utilization. We will also divide patients into groups based on their participation in the Joyable program and compare outcomes (e.g., PHQ-9 score, quality of life, health utilization) between subjects who showed high engagement in the program and those who showed low engagement.

Table 2. Statistical Power for single sample paired t-test

SD of the Difference	Difference in PHQ-9 Pre/Post Treatment				
	1	2	3	4	5
2	61%	99%	100%	100%	100%
3	32%	85%	99%	100%	100%
4	20%	61%	92%	99%	100%
5	15%	43%	77%	95%	99%
6	12%	32%	61%	85%	96%

Data Confidentiality

Internet-based files will only be made available to personnel involved in the study through the use of access privileges and passwords. Paper-based records will be kept in a locked, secure location and only accessible to study personnel. Prior to access to any study-related information, personnel will be required to sign statements agreeing to protect the security and confidentiality of identifiable information. Whenever feasible, identifiers will be removed from study-related information.

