 I am unable to wash or dress myself

Usual Activities (e.g. work, study, housework, family or leisure activities)

[figure not shown]
I have no problems with performing my usual activities
 I have some problems with performing my usual activities
 I am unable to perform my usual activities

Pain/Discomfort

I have no pain or discomfort
 I have moderate pain or discomfort
 I have extreme pain or discomfort

Anxiety/Depression

I am not anxious or depressed
 I am moderately anxious or depressed
 I am extremely anxious or depressed

YOUR HEALTH TODAY =

5. Healthcare Utilization

Since study enrollment:

How many times did you visit a **physician**? Do **not** include visits while in the hospital or to a hospital emergency room. Fill in with “0” or another number. _____ times

How many times did you go to a **hospital** emergency room? Fill in with “0” or another number. _____ times

How many different **times** did you stay in a hospital **overnight** or longer in the past 6 months? Fill in with “0” or another number. _____ times

How many total **nights** did you spend in the hospital? Fill in with “0” or another number. _____ nights

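### Healthcare utilization is compared between groups defined by a PHQ-9 taken after most of that utilization has occurred, so the hypothesized direction could arise with no effect of depression on utilization

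*Combined protocol and SAP*

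**What the plan says.** The comparison is in the Analysis Plan, in the paragraph before Table 2. It is labelled exploratory and defines the groups by the final score: "we will divide patients into two groups based on PHQ-9 at study completion". The cut is at the sample median, with the high group "defined as median or above". The plan continues: "Healthcare outcomes, including modified Rankin scale, health related quality of life, and healthcare utilization will be compared across groups". It then gives a direction: "We hypothesize that patients with high depression symptoms will have worse functional outcome, lower quality of life, and higher healthcare utilization". No test is named.

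The 90 Day In-person Visit section collects "healthcare utilization using the Stanford Health Utilization survey" at the same visit as the final PHQ-9, and Table 1 shows the survey at no other time. In the Appendix (90 Day Visit CRF, item 5) the utilization questions stand under the heading "Since study enrollment". The overnight-stay question under that heading, however, asks about the preceding six months. The PHQ-9 in item 6 of the same form has a two-week recall.

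The paragraph also plans a comparison of outcomes, including utilization, "between subjects who showed high engagement in the program and those who showed low engagement".

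**The concern.** Utilization is treated as an outcome of the symptom groups, yet the groups are formed from a score that comes later than most of the events counted. Illness during follow-up can both put a subject in hospital and raise the PHQ-9 at the end. Such a subject moves into the high-symptom group because of the stay, and the stay then counts as evidence that the high-symptom group uses more care.

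The Analysis Plan does not mention this possibility. For this comparison it does not use the enrollment PHQ-9, use the weekly in-program scores to order events, or adjust for baseline severity. What is at stake is the reading of one exploratory result: a pattern that agrees with a hypothesis written in advance, in a pilot meant to give preliminary evidence, could be carried forward as support for it.

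The modified Rankin scale and the EQ-5D are measured at the same visit as the grouping score. Those comparisons are cross-sectional, not reversed in time.

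**Working it through.** The plan gives no effect size, power or test for this comparison, so there is no figure to reproduce. Table 2 concerns the paired pre/post PHQ-9 test and does not bear on the point.

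**Step 1: time order, from the documents.** The visit falls at 90 ± 14 days, that is, day 76 to day 104. The PHQ-9 window is the last 14 days. The share of the since-enrollment period that precedes it is (visit day − 14) / visit day:

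- day 76: 62/76 = 82%
- day 90: 76/90 = 84%
- day 104: 90/104 = 87%

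The overnight-stay item reaches further back. Taking six months as about 183 days, it extends before enrollment by 183 − 104 = 79 to 183 − 76 = 107 days. The exclusion criteria provide for subjects enrolled as inpatients, so the item can count the index stroke admission. The question on total nights follows it with no period of its own.

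**Step 2: how large a spurious difference could be.** None of these inputs is in the documents; all are assumptions.

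- 20 subjects; enrollment PHQ-9 normal with mean 11 and SD 3.5 to 4, limited to 5-19.
- Each subject has a stay with probability 0.20, independent of the enrollment score. Depression has no effect on hospitalization.
- Day-90 PHQ-9 = 7 + 0.5 × (enrollment − 11) + normal error (SD 3.9) + shift if hospitalized, rounded and bounded at 0-27.
- Split as planned, median or above against below.

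| Assumed rise in Day-90 PHQ-9 after a stay | Hospitalized, high v low group | High group has the higher rate | Fisher's exact test rejects at 5% |
|---|---|---|---|
| 0 points | 20% v 20% | about 44% of trials | not above nominal |
| 2 points | 25% v 14% | about 68% | about 2% |
| 3 points | 27% v 11% | about 79% | about 4% |
| 5 points | 31% v 6-7% | about 91% | about 11% |

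The 44% is below one half because some trials have equal rates in the two groups. Grouping the same subjects by enrollment PHQ-9 gives 20% v 20%.

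Arithmetic check: ties at the median put about 10.8 subjects in the high group and 9.2 in the low. At 3 points, 0.27 × 10.8 + 0.11 × 9.2 = 2.9 + 1.0 = 3.9 stays, against 0.20 × 20 = 4 expected.

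**Step 3: why significance is rare.** With four hospitalized subjects, even all four falling in the high group does not reach 5%. In an 11/9 split the two-sided Fisher p is [C(11,4) + C(9,4)] / C(20,4) = (330 + 126)/4845 = 0.094. In a 10/10 split it is 2 × 210/4845 = 0.087.

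**Step 4: sensitivity.** A simpler model (Day-90 PHQ-9 with mean 8 and SD 4.5) gives, at 10%, 20% and 30% hospitalized:

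- 3-point rise: 14% v 5%, 27% v 12%, 40% v 19%
- 5-point rise: 16% v 3%, 31% v 7%, 45% v 12%

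The high group has the higher rate in 64% to 94% of these trials.

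**The case against.** The strongest reply has four parts.

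- *The hypothesis is associational and exploratory.* This stands. The plan does not say in words that depression causes utilization, and a reader who infers that claim goes beyond the text. But a direction is stated, utilization is called an outcome, and nothing warns that the association could run the other way. Exploratory status excuses low power; it does not put the exposure before the outcome.
- *The simulation assumes reverse causation and then recovers it.* This also stands. It shows what could happen and roughly how large it would be, not that it will happen. A reader might also infer a substantial risk of a false significant result. The planned split does not support that: at 20 subjects Fisher's exact test rejects at or below the nominal rate for rises of 2 and 3 points. Testing the continuous score would reject more often, but the plan names no such test.
- *Residual symptoms at completion are a legitimate question.* They are, and the 90-day comparison can stay as description.
- *The engagement comparison does not have the same fault.* A reader might infer that it does, on the ground that a hospitalized subject cannot use the program. The documents do not support this. Inpatients may be enrolled, subjects are asked to complete activities at enrollment, and a study tablet is provided for enrolling those without a device. The program lasts 8 weeks (56 days) and the final PHQ-9 and EQ-5D come no earlier than day 76, after its planned end. What remains is narrower: engagement and utilization accrue over overlapping follow-up, so that one comparison has no clear time order.

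**Conclusion.** The concern holds for the utilization comparison. The documents themselves show that at least 82% of the since-enrollment period precedes the mood window that defines the groups, and more for overnight stays as that item is now worded. Under the assumed inputs the spurious gap in the share hospitalized is about 11, 16 and 24-25 percentage points for rises of 2, 3 and 5 points (25 − 14, 27 − 11, 31 − 7 or 31 − 6). The likely harm is a misleading direction in line with the stated hypothesis.

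The time order rests on the documents alone. The sizes rest on an assumed 20% hospitalization rate, assumed effects of a stay on the later score, and assumed score distributions. Severity is minor to moderate: the analysis is exploratory in a 20-subject pilot, and neither primary outcome nor Table 2 depends on it.

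**What to change.** 1. In the Analysis Plan, relate post-enrollment utilization to the enrollment PHQ-9 as a continuous score. It is already collected and precedes follow-up utilization.
2. Keep the 90-day median split as a cross-sectional description, and drop the directional hypothesis for utilization from it.
3. Reconcile the overnight-stay question in item 5 of the 90 Day Visit CRF with its heading, so that it counts only stays after enrollment, and give the total-nights question the same period. Until this is done, step 1 does not restore time order for hospital stays. If the form is already in use, counts recorded under the six-month wording cannot be split afterwards and should be reported as such.
4. Label the engagement-utilization comparison descriptive. Measuring engagement to day 30 and utilization only after it is not possible with the planned data: utilization is an undated total taken once, at the 90-day visit. It would need dated events or the survey added to the 30-day call.

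Steps 1, 2 and 4 cost a few sentences; step 3 costs a CRF revision. The drawbacks are that the enrollment score is restricted to 5-19, which narrows its range, and that it answers a question about severity at enrollment, not residual symptoms. It restores time order but does not remove confounding by stroke severity.

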Secondary outcome variables will include: completion of the iCBT program, number of telephone/email based coaching interactions, quality of life, measured using the EuroQOL-5D

(EQ-5D), healthcare utilization, measured using the Stanford Health Care Utilization Survey, and subject satisfaction with the program.

Background

Depression after stroke

Depression is common after stroke, occurring in up to one-third of all stroke patients.¹ A recent American Heart Association (AHA) scientific statement on post-stroke depression highlighted the importance of this condition, noting that it was “under-recognized, under-investigated, and under-treated.”² Individuals with depression after stroke have been shown to have lower functional status and lower quality of life than those without depression, irrespective of stroke severity, although the independent contribution of depression on outcomes is still not fully understood.

Traditional Cognitive Behavioral Therapy

Cognitive behavioral therapy (CBT) is an effective treatment for common mood disorders. Studies have shown a beneficial effect of CBT for both the treatment and prevention of depression after stroke.^{3,4} There is also evidence suggesting that CBT may provide a more durable and lasting treatment effect than pharmacotherapy with selective serotonin reuptake inhibitors.⁵

Despite the promise of CBT, its role in routine clinical practice is limited. There are significant barriers to widespread use of CBT. First, access to experienced CBT practitioners is limited.⁶ Second, the time and travel requirements to complete a course of CBT, which may require 2-3 visits per week for 10-12 weeks, are onerous for many patients. This may be even more difficult for patients with mobility limitations, which are common after stroke. Third, the cost of CBT may be prohibitive, particularly if providers do not accept insurance.⁶ Finally, patients may be resistant to in-person CBT because of stigma or fear of sharing deeply personal feelings with a therapist.

Technology and CBT

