For patients who are enrolled, basic demographic and clinical information will be collected including: age, sex, race/ethnicity, past medical history (including history of hypertension, hyperlipidemia, coronary artery disease, chronic kidney disease, prior history of TIA/Stroke, prior history of anxiety, depression, or PTSD, other medical history), educational attainment, insurance status, marital status, number of people living in the home, medication history (current/prior use of an antidepressant medication), current/prior participation in psychotherapy or counseling for mental health problems, tobacco history (current smoker, former smoker, never smoker), alcohol use history (current alcohol use yes/no and if yes, number of drinks per week), stroke location, stroke mechanism (large vessel atherosclerosis, small vessel disease, cardioembolism, other, cryptogenic), discharge disposition (home, acute rehab).

Additional assessments will include the NIHSS, a structured neurologic examination used to quantify neurologic deficits,^{16, 17}, modified Rankin Scale,¹⁸ the Patient Health Questionnaire-9 (PHQ-9) to assess mood,¹⁵ and the abbreviated Duke Social Support Index.¹⁹ We will also ask the subject a series of questions regarding availability of internet and mobile device usage, including how they interact with the internet and frequency of internet use (See attached appendix).

After baseline data collection, the subjects will be enrolled in Joyable's iCBT program. For subjects who would like to participate in the program using their smartphone, the CBT application will be installed on their device and they will be encouraged to complete the initial

evaluation and activities at the time of enrollment. Subjects without their own device will be enrolled via a study specific tablet using the web-interface. Subjects will be given their login information and information on how to access the program via the internet and install the program on their mobile device. Subjects will be asked to complete the initial evaluation and CBT activities at the time of enrollment.

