24. NIHSS

Date: month / day / 20 year

1a. Level of consciousness
 
0 alert 1 drowsy 2 stuporous 3 coma
 
1b. LOC questions (month, age)
 
0 both correct 1 one correct 2 incorrect
 
1c. LOC commands (close eyes, make a fist)
 
0 both correct 1 one correct 2 incorrect
 
2. Best gaze
 
0 normal 1 partial gaze palsy 2 forced deviation
 
3. Visual fields
 
0 no visual loss 1 partial hemianopia 2 complete hemianopia 3 bilateral hemianopia
 
4. Facial palsy
 
0 normal 1 minor 2 partial 3 complete
 
5. Motor arm
 
a. Left arm
 
0 no drift 1 drift 2 can't resist gravity 3 no effort against gravity 4 no movement Z amputation/joint fusion
 
b. Right arm
 
0 no drift 1 drift 2 can't resist gravity 3 no effort against gravity 4 no movement Z amputation/joint fusion
	
6. Motor leg
 
a. Left leg
 
0 no drift 1 drift 2 can't resist gravity 3 no effort against gravity 4 no movement Z amputation/joint fusion
 
b. Right leg
 
0 no drift 1 drift 2 can't resist gravity 3 no effort against gravity 4 no movement Z amputation/joint fusion
 
7. Limb ataxia (FNF, HKS)
 
0 absent 1 present in one limb 2 present in 2 limbs
 
8. Sensation (pin)
 
0 normal 1 partial loss 2 severe loss
 
9. Best language
 
0 no aphasia 1 mild-mod aphasia 2 severe aphasia 3 mute
 
10. Dysarthria
 
0 none 1 mild-mod 2 near to unintelligible or worse/mute Z intubated/barrier
 
11. Extinction and inattention
 
0 no neglect 1 partial neglect 2 complete neglect
 
Total Score: _____

---	--

25. Modified Rankin Scale

Score	Description
0	No symptoms at all
1	No significant disability despite symptoms; able to carry out all usual duties and activities
2	Slight disability; unable to carry out all previous activities, but able to look after own affairs without assistance
3	Moderate disability; requiring some help, but able to walk without assistance
4	Moderately severe disability; unable to walk without assistance and unable to attend to own bodily needs without assistance
5	Severe disability; bedridden, incontinent and requiring constant nursing care and attention
6	Dead

TOTAL (0–6): _____

26. Euro-QOL-5D

Please indicate which statements best describe your own health state today.
Mobility

I have no problems in walking about
 I have some problems in walking about
 I am confined to bed

Self-Care

I have no problems with self-care

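### The exploratory Day-90 comparison of function, quality of life and utilization by PHQ-9 group uses no baseline value, so it cannot separate depressive symptoms from disability already present at enrollment

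*Combined protocol and SAP*

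**What the plan says.** The comparison is in the Analysis Plan, in the exploratory paragraph just before Table 2. The grouping is made on the final score: "we will divide patients into two groups based on PHQ-9 at study completion", with scores at or above the median called high and the rest low. Then: "Healthcare outcomes, including modified Rankin scale, health related quality of life, and healthcare utilization will be compared across groups". The expected direction is stated: "We hypothesize that patients with high depression symptoms will have worse functional outcome, lower quality of life, and higher healthcare utilization". No test, covariate, change score or stratification is named.

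The baseline data exist. Study Procedures, Baseline says: "Additional assessments will include the NIHSS, a structured neurologic examination used to quantify neurologic deficits", and lists the modified Rankin Scale with it. Table 1 marks NIHSS, mRS and EQ-5D at baseline, and the Baseline CRF carries them as items 24 to 26 (for example "25. Modified Rankin Scale"). EQ-5D is not named in the Baseline text but is in both Table 1 and the CRF. Utilization is different: the 90-day visit collects "healthcare utilization using the Stanford Health Utilization survey", and Table 1 shows no baseline value.

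The only analytic use stated for baseline clinical factors is against adherence: "In an exploratory analysis we will look for relationships between baseline clinical and demographic factors and number of activities completed".

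The Background (Depression after stroke) reports worse function and quality of life in depressed patients whatever the stroke severity, then adds: "although the independent contribution of depression on outcomes is still not fully understood".

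**The concern.** PHQ-9 group and outcome are measured at the same visit, and both may depend on how disabled the subject was at enrollment. Enrollment takes in inpatients and clinic outpatients, discharged home or to acute rehabilitation, so enrollment disability will vary. Several PHQ-9 items (tiredness, concentration, slowed movement or speech) can reflect neurologic deficit as well as mood. A gap between the groups could then arise from enrollment disability, from depressive symptoms, or from both, and the comparison as written cannot tell which.

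The risk lies in interpretation. The pilot is meant to inform later work, and a reader who has seen the Background may take a positive result as evidence on the question left open there. The problem does not depend on where PHQ-9 is cut; it remains if PHQ-9 is kept continuous.

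**Working it through.** **Inputs from the documents.** n = 20 (Sample Size), so about 10 per group if there are no dropouts or ties. Alpha = 0.05 is stated for Table 2 only. No power or error figure is given for this comparison. Table 2 concerns the pre/post PHQ-9 change and is used here only to confirm the setting: at difference 3 and SD 4, Φ(3×√20/4 − 1.96) = Φ(1.394) = 91.8%, against 92% printed. A two-sided 5% level with n = 20 is therefore the plan's own convention.

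**Inputs assumed.** Let r1 be the correlation of enrollment function with Day-90 PHQ-9, and r2 its correlation with the Day-90 outcome. The documents give neither. The range taken is r1 = 0.3 to 0.5 and r2 = 0.6 to 0.8, with r1 = 0 as reference. PHQ-9 and outcome have no direct link.

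**Formula.** A median split of a standard normal score puts the group means at ±√(2/π) = ±0.798, a gap of 1.596 SD. With no direct link the correlation of PHQ-9 with outcome is r1×r2, so the expected outcome gap is 1.596×r1×r2:

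- r1 = 0.3, r2 = 0.6: 1.596×0.18 = 0.29 SD
- r1 = 0.5, r2 = 0.8: 1.596×0.40 = 0.64 SD

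**Simulation.** 20 subjects, 40,000 replicates per row. The unadjusted analysis is a t-test between the groups; the adjusted one adds enrollment function as a single covariate (17 residual degrees of freedom instead of 18). Higher scores are worse.

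| r1 | r2 | Gap by formula (SD) | Simulated gap (SD) | In hypothesized direction | p<0.05 unadjusted | p<0.05 adjusted |
|---|---|---|---|---|---|---|
| 0 | 0.7 | 0 | 0.00 | 50% | 4.9% | 4.9% |
| 0.3 | 0.6 | 0.287 | 0.28 | 73% | 9.2% | 4.9% |
| 0.3 | 0.8 | 0.383 | 0.37 | 80% | 12.4% | 5.2% |
| 0.5 | 0.6 | 0.479 | 0.46 | 85% | 17.1% | 5.1% |
| 0.5 | 0.8 | 0.638 | 0.61 | 93% | 27.5% | 4.7% |

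Shorter runs of 3,000 to 6,000 replicates put the last unadjusted figure between 27% and 29%. With PHQ-9 kept continuous, the unadjusted figures run from 12% to 43%.

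**Checks on the adjusted column.** A 5-level ordinal outcome and baseline with an integer PHQ-9 give 10% to 26% unadjusted and 5.0% to 5.8% adjusted, so coarse scoring alone does not defeat the adjustment. Measurement error does weaken it. With continuous PHQ-9 and a baseline measure of assumed reliability 0.6, adjusted rejection still reaches about 15% at the worst corner; at reliability 0.8 it reaches about 8%.

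**The case against.** The strongest reply is that the analysis is exploratory and its hypothesis is an association. It claims neither independence nor cause. If disability drives both PHQ-9 and outcome, high-PHQ-9 subjects really do have worse outcomes, and finding so is correct. Neither study objective (adherence; pre/post change in symptoms and quality of life) depends on this comparison. This stands: a reader might infer from the table that the plan carries a false-positive rate of up to 28% for its stated hypothesis, and the documents do not support that. The excess applies only to a reading as an independent effect.

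Three further points stand.

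- The correlations are assumed, and at r1 = 0 the distortion vanishes. The omission is certain; its size is not.
- The plan is silent on method and does not rule out adjustment. Silence in the analysis section still leaves that choice until the data have been seen.
- Adjustment has its own weakness. All subjects enter with PHQ-9 of 5 to 19, and EQ-5D contains an anxiety/depression item, so baseline EQ-5D and mRS may already reflect depression. Conditioning on them may remove part of the association of interest. This argues for showing both results, not for omitting the adjusted one.

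**Conclusion.** The point holds as a modest, cheaply corrected weakness in an exploratory analysis. The comparison uses no baseline value although three relevant ones are collected, and it cannot separate depressive symptoms from disability present at enrollment. Under the assumed correlations and no direct link, the apparent gap is about 0.3 to 0.6 SD, with p<0.05 in about 9% to 28% of trials. These figures assume normal scores, a single confounder and no dropout.

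Three stronger readings should be resisted.

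- A reader might take the confounder to be initial stroke severity. The baseline measures describe status at enrollment, which as printed may be up to 63 months after the stroke.
- A reader might conclude from the 5% in the adjusted column that adjustment isolates the effect of depression. That figure follows from simulating one confounder measured without error; age, prior depression and antidepressant use would remain open.
- A reader might expect a reliable gain in power. A rise from 37% to 59% (true slope 0.4, baseline correlation 0.7 with outcome, continuous PHQ-9) holds only without confounding, so it cannot be claimed alongside this concern.

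**What to change.** In the exploratory paragraph of the Analysis Plan:

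- Keep the unadjusted comparison and label it descriptive.
- Beside it, report a model of each Day-90 outcome on Day-90 PHQ-9 group plus one baseline covariate: baseline mRS for mRS; baseline EQ-5D, scored the same way at both visits, for EQ-5D; and baseline mRS as a proxy for utilization, which has no baseline value. One covariate per model is a sensible limit with 20 subjects.
- Give both estimates with 95% confidence intervals.
- State that adjustment reduces but does not remove confounding (measurement error, other confounders), and that baseline EQ-5D and mRS may already reflect depression, so the adjusted estimate may omit part of the association.

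The cost is a few sentences in the plan and one degree of freedom per model. No new data are needed.
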